## **Protocol Summary**

This document represents the protocol summary for the study on human subjects. The study will be carried out in accordance with ICH GCP, National Standard of the Russian Federation GOST 52379-2005 "Good Clinical Practice", Helsinki Declaration of World Medical Association, relevant requirements of the regulatory authorities as well as the study procedures.

## **Title of Study**

International Multicenter Double-blind Placebo-Controlled Parallel-Group Randomized Clinical Trial of Efficacy and Safety of Ergoferon in the Treatment of Acute Respiratory Viral Infections in Children.

**Phase:** IV

**Sponsor:** OOO "NPF "Materia Medica Holding", Moscow, Russia

**Protocol No.** MMH-ER-009

## **Objective of the study**

- To obtain additional data on the efficacy and safety of Ergoferon in therapy of acute respiratory viral infections (ARVI) in children aged 6 months to 6 years old.

## **Endpoints**

### **Primary endpoint**

1. Time to alleviation of all ARVI symptoms (time from enrollment in the study to alleviation of all ARVI symptoms, according to the patient's diary).

### **Secondary endpoints**

1. Time to normalization of body temperature.
2. Time to alleviation of flu-like nonspecific symptoms.
3. Time to alleviation of respiratory symptoms.
4. Flu-like nonspecific and respiratory symptoms total score (TS) for days 2-6 (according to the patient's diary).
5. ARVI severity (based on the area under the curve of TS for days 2-6, according to the patient's diary).
6. Percentage of patients recovered on day 2, 3, 4, 5, and 6 (according to the patient's diary).

---

 Criteria of alleviation of all ARVI symptoms: body temperature  $\leq 37.5^{\circ}\text{C}$  for 24 hours (without subsequent increase within the observation period) + absence of ARVI symptoms /presence of ARVI symptoms with  $\leq 3$ -point of TS.

 Oral temperature  $\leq 37.5^{\circ}\text{C}$  for 24 hours (without subsequent increase within the observation period).

 Absence of flu-like nonspecific symptoms/presence of one mild flu-like nonspecific symptom.

 Absence of respiratory symptoms/presence of one mild respiratory symptom.

7. Rates of antipyretic use per patient during days 1 to 5 of therapy (according to the patient's diary).
8. Percentage of patients with worsening of illness (ARVI complications, including those requiring antibiotics; hospitalization) for 14 days.

### **Safety assessment**

- Presence and type of adverse events during the therapy, their severity, relation to investigational drug, outcomes.
- Dynamics of vital signs.

### **Study design**

Study design: multicenter double-blind placebo-controlled randomized clinical study in parallel groups.

The study will enroll patients of either gender aged from 6 months to 6 years old with clinical manifestations of ARVI within the first day after the onset of the disease. Patients will be included evenly (1:1 ratio) in accordance with the age group: 6 months – 3 years 11 months 29 days; 4 years – 6 years 11 months 29 days. Signed information sheet for parents/adopters (informed consent form) will be obtained from all participants' parents/adopters prior to the screening procedures.

Medical history, thermometry, patient examination by a doctor, assessment of ARVI symptoms severity, and nasopharyngeal swabs will be performed at screening visit (Day 1). If the inclusion criteria are met and exclusion criteria are absent, the patient is included in the study.

Nasopharyngeal swabs will be analyzed by real-time reverse transcription polymerase chain reaction (RT-PCR) to identify the most common respiratory viruses, including (1) Influenza A virus; (2) Influenza B virus; (3) Influenza A (H1N1)pdm; (4) Human metapneumovirus; (5) Human respiratory syncytial virus; (6) Human rhinovirus; (7) Human adenovirus; (8) Human bocavirus; (9) Human parainfluenza virus 1; (10) Human parainfluenza virus 2; (11) Human parainfluenza virus 3; (12) Human parainfluenza virus 4; (13) Human coronavirus OC43; (14) Human coronavirus 229E; (15) Human coronavirus HKU1; (16) Human coronavirus NL63.

Patients are randomized into one of two groups: the 1st group patients will take Ergoferon according to the dosage regimen for 5 days; the 2nd group patients will take Placebo according to the dosage regimen of Ergoferon for 5 days.

Patient's parents/adoptive parents are provided with diaries where daily in the morning and at night they record oral temperature (measured by a digital thermometer provided by Sponsor), symptoms of ARVI (according to the 4-point scale), administered drug and concomitant therapy. Doctors instruct parents/adoptive parents how to fill in diaries; the first scores of ARVI

symptoms severity and oral temperature are made by doctors together with the parents/adoptive parents.

Patients are observed up for 14 days (screening and randomization up to 1 day, therapy for 5 days, follow-up from 6 to 10 day; delayed telephone “visit” on day 14). During the observation period two visits are planned (at home or at the medical center) on day 3 (Visit 2) and day 6 (Visit 3). If patients still have any symptoms of ARVI/complications of ARVI, then an additional (unscheduled) Visit 4 is held on Day 10 of the observation (at the medical center). During Visits 2, 3 (4), doctors carry out an physical examination, record dynamics of ARVI symptoms and concomitant therapy, check patient’s diaries, which parents/adoptive parents return back at Visit 3 or 4. At Visit 3 (after 5 days of therapy), compliance with the treatment is additionally assessed. A “telephone visit” (Visit 5, Day 14 ± 1) is carried out to interview parents about the patient’s condition, presence/absence of complications, and possible use of antibiotics. During the study, symptomatic therapy and therapy for underlying chronic conditions are allowed with the exception of the drugs indicated in the section “Prohibited Concomitant Treatment”.

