## **Inclusion and exclusion criteria**

### ***Inclusion criteria***

1. Patients of both genders aged 6 months to 6 years old.
2. ARVI based on medical examination: oral temperature of at least 38.0°C at the time of examination + total symptom severity ≥5 points.
3. First 24 hours after ARVI onset.
4. Seasonal rise in ARVI incidence.
5. Availability of signed information sheet for parents/adopters (informed consent form) for participation in the clinical trial.

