#### *Parametric criteria*

The application of parametric criteria will be accompanied by a check for normality of the compared samples (Kolmogorov-Smirnov test).

The following parametric methods and approaches are supposed to be used:

1. To assess the differences of continuous variables obtained in two different (independent) groups – Student t-test for independent samples.
2. To assess the differences of continuous variables obtained in one group at two different visits – Student t-test for for paired samples.
3. To assess the temporal dynamics of the compared indicators – analysis of variance (ANOVA) or covariance (ANCOVA) in the modification with repeated measures.
4. In case of multiple comparisons between the groups will apply a variety of corrections for multiplicity (Dunnett), (Tukey), (Scheffe), Holm adaptive test, etc.
5. In case of abnormal data distribution, approaches with the Generalized Linear Models and / or Mixed Linear Models will be used.
6. Selection of the type of distribution, clarification of the factor and covariance structures of the model is carried out with fit statistics such as AIC (Akaike information criterion).

To perform the above-mentioned statistical tests and techniques, it is assumed that the following SAS procedures are used:

- UNIVARIATE – check for normality of the compared distributions;
- CORR, MEANS – calculation of descriptive statistics;
- TTEST – Student t-test with all the modifications;
- GLM – analysis of Generalized Linear Models for studying temporal dynamics (ANOVA, ANCOVA);
- GENMOD – analysis of Generalized Linear Models.  
MIXED – analysis of Generalized Linear Models.

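### Optional improvement: age group and Day 1 severity are known for every eligible child, but no listed analysis names them as covariate or stratum

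*Combined protocol and SAP*

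**What the plan says.** **Baseline data.** The combined protocol and SAP (Study design) states "Patients will be included evenly (1:1 ratio) in accordance with the age group", with two groups divided at the fourth birthday. The same section says "assessment of ARVI symptoms severity, and nasopharyngeal swabs will be performed at screening visit (Day 1"), before the child is included. Entry requires "oral temperature of at least 38.0°C at the time of examination + total symptom severity" of 5 points or more (Inclusion criteria, item 2). The first diary entries for "symptoms severity and oral temperature are made by doctors together with the parents/adoptive parents" (Study design), so a Day 1 value exists in the same diary that supplies the later outcomes.

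**Outcomes.** The primary endpoint is "Time to alleviation of all ARVI symptoms". Secondary endpoint 4 is "Flu-like nonspecific and respiratory symptoms total score (TS) for days 2-6", item 5 is the area under that curve, and item 6 is the percentage recovered on each of days 2 to 6.

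**Analysis.** For a continuous variable in two independent groups the plan lists "Student t-test for independent samples" (Parametric criteria, item 1) or the Mann-Whitney test (Non-parametric criteria, item 1). For change over time it lists "analysis of variance (ANOVA) or covariance (ANCOVA) in the modification with repeated measures" (Parametric criteria, item 3). Items 5 and 6 add generalized and mixed models, with distribution and structure settled by fit statistics such as AIC. Non-parametric criteria add the Cochran-Mantel-Haenszel (CMH) test for independent strata and survival analysis. None of these names age group, Day 1 score, Day 1 temperature or any other baseline variable.

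**The concern.** When means are compared, any outcome variance that baseline values explain stays in the error term. The interval for the treatment difference is then wider than the collected data require. The day 2-6 total score and its area under the curve matter most here, because the Day 1 score is an earlier value of the same measure.

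There is also a question of pre-specification. A method list that includes ANCOVA and CMH without terms leaves the choice of covariates and strata open. Item 6 of the parametric list could be read as letting fit statistics settle some of that choice. Naming the terms in advance closes the question.

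**Working it through.** **Inputs from the plan** (Evaluation of sample size; Assumptions about the expected effects): two-sided alpha 0.05, power 80%, difference 0.5 day, SD 1.3 days, 108 per arm for the per-protocol analysis, 144 per arm enrolled.

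**Inputs not in the plan, assumed here:** R2 of the baseline terms with time to alleviation, the correlation of Day 1 score with later score, and the difference in mean time between age groups.

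**1. The plan's own figure.** The normal approximation is n = 2 x [SD x (1.960 + 0.842) / d]^2 = 2 x (1.3 x 2.802 / 0.5)^2 = 106.1, so 107 per arm. The exact t calculation gives power 79.97% at 107 and 80.3% at 108, so 108 reproduces. Then 108 / (1 - 0.25) = 144 per arm, 288 in total. (The formula as printed lacks the factor 2 and would give 53.1. The stated 108 is right for a two-sample t-test, and that is a separate matter.)

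**2. Mean time to alleviation with adjustment.** Residual SD = 1.3 x sqrt(1 - R2). Power is from the noncentral t distribution. The 95% half-width is t x SD x sqrt(2/n), with t = 1.971 at n = 108.

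| Assumed R2 | Residual SD (days) | Power, 108 per arm | Half-width, 108 per arm (days) | Power, 144 per arm |
|---|---|---|---|---|
| 0 | 1.300 | 80.3% | 0.349 | 90.2% |
| 0.02 | 1.287 | 81.1% | 0.345 | 90.8% |
| 0.05 | 1.267 | 82.3% | 0.340 | 91.6% |
| 0.10 | 1.233 | 84.3% | 0.331 | 92.9% |
| 0.20 | 1.163 | 88.2% | 0.312 | 95.3% |

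In minutes, the half-width at 108 per arm falls by (0.3487 - 0.3452) x 1440 = 5 at R2 0.02, by (0.3487 - 0.3399) x 1440 = 13 at 0.05, and by (0.3487 - 0.3119) x 1440 = 53 at 0.20. The degrees of freedom spent on covariates change power by about 0.0001.

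**3. Age group alone.** With two equal groups whose mean times differ by g days, the share of variance is (g^2 / 4) / 1.69. For g = 0.25 this is 0.009 and power at 108 per arm is 80.7%. For g = 0.5 it is 0.037 and power is 81.8%.

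**4. Effect of the entry threshold.** Requiring 5 points or more cuts off the low end of the severity range. If the score were normal and the threshold removed the lowest 10%, 30% or 50%, its variance would shrink by u = 0.712, 0.493 or 0.363. With R2' = R2 x u / (1 - R2 + R2 x u), an R2 of 0.20 in unselected children becomes 0.15, 0.11 or 0.08.

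**5. Total score and area under the curve, days 2-6.** With correlation r between Day 1 and later score, the interval is multiplied by sqrt(1 - r^2). At r = 0.2, 0.3 and 0.5 the factor is 0.980, 0.954 and 0.866, so the interval is 2.0%, 4.6% and 13.4% narrower.

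No gain was calculated for the stratified log-rank test or for CMH. Those choices rest on the age-balanced enrolment and not on a computed size.

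**The case against.** The strongest reply is that nothing is wrong: the unadjusted comparison is valid and powered, and whether the adjusted or unadjusted result leads is a design preference. That stands, and it is why the point is optional.

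It can also be said that adjustment is already partly provided for. Repeated-measures ANCOVA could cover the daily total score, where the gain is most plausible, and CMH is listed. This also stands. What remains is to name the terms. The document describes itself as a protocol summary, so a fuller plan may already do this.

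Third, the size rests on assumed correlations, and 108 per arm is the per-protocol figure. The Full Analysis Set may be larger, and the gain is then smaller: at R2 0.05 it is 2.0 points of power at 108 per arm and 1.4 at 144. Both sizes are shown for that reason. The actual size of the Full Analysis Set is unknown, because the 25% allowance also covers exclusions at screening.

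Stronger readings that a reader might draw, and that the documents do not support:

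- **The survival analysis is unstratified.** The plan lists survival analysis in general terms and neither names nor excludes strata.
- **Randomization is stratified by age and the analysis ignores it.** The age sentence may describe only an enrolment quota. The plan does not say that allocation is stratified.
- **Baseline covariates will be picked by AIC.** Item 6 follows the generalized and mixed models of item 5 and does not clearly govern the ANCOVA of item 3.
- **A covariate-adjusted hazard model would bring a larger gain.** It estimates a conditional hazard ratio, which is a different target from the marginal one. Diaries are completed twice a day, so event times would be heavily tied. It is a trade-off and not a free gain, and it is not proposed here.

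**Conclusion.** The point holds as an optional improvement. Baseline variables that the trial must collect to judge eligibility are named in no listed analysis, and naming them costs almost nothing. The most plausible benefit is on the day 2-6 total score and area under the curve (2.0% to 13.4% narrower at correlations of 0.2 to 0.5). For the primary endpoint, if means are compared, the benefit may be only 5 to 13 minutes of half-width at R2 0.02 to 0.05 and 108 per arm. The upper end of the range, R2 0.20, is less likely after the entry threshold. Every size depends on assumed R2 or correlation, and the mean-time figures also depend on the plan's 0.5 day difference and 1.3 day SD. A reader should not infer that the trial is underpowered or that its planned test is invalid: the stated 108 and 288 reproduce, and the unadjusted test reaches its target.

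**What to change.** Add a few lines to the analysis section, when the primary method is assigned, or confirm that a fuller plan already contains them:

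- **Total score and area under the curve, days 2-6:** ANCOVA with Day 1 total score and age group.
- **Primary endpoint:** the same ANCOVA if mean times are compared. If survival analysis is used, a log-rank test stratified by age group.
- **Percentage recovered on days 2 to 6:** CMH stratified by age group.
- **Day 1 temperature:** may be added to the ANCOVA, though entry truncates it at 38.0°C and its separate contribution has not been estimated.
- **Definition:** say which Day 1 score is the covariate (screening assessment or first diary entry) and that it precedes the first dose.
- **Pre-specification:** state that these terms are fixed in advance and are not chosen by AIC.
- **Supporting analysis:** keep the unadjusted comparison.

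The cost is text only. No new data, visits or patients are needed, and the sample size stays as it is.

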### ***Observation period***

In total, the patient is observed up for 14 days (screening and randomization up to 1 day, therapy for 5 days, follow-up from 6 to 10 day; delayed telephone “visit” on day 14).

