### Study design scheme

### Schedule of study procedures

Procedure/ Visit	Visit 1 (Day 1)	Visit 2 (Day 3)	Visit 3 (Day 6)	Visit 4* (Day 10)	Visit 5 (Day 14±1)
Informed consent	+				
Collection of complaints	+	+	+	+	
Medical history	+				
Physical examination	+	+	+	+	
ARVI symptoms registration	+				
Inclusion/exclusion criteria	+				
Concomitant therapy	+	+	+	+	+
Nasopharyngeal swabs for RT-PCR	+				
Randomization and prescription of study drug	+				
Study drug supply	+				
Antipyretics	+				
Study drug accountability, compliance assessment			+		
Diary supply	+				
Checking the correctness of filling the diary		+	+	+	
Diary return			+	+	
Evaluation of treatment safety	+	+	+	+	
Telephone survey					+

\* Visit 4 – unscheduled (additional), provided if the patient still experiences the ARVI symptoms/ complications

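### The no-rebound rule behind the primary endpoint is checked to Day 6 in symptom-free children but to Day 10 in the others; one diary end date for all would fix this

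*Combined protocol and SAP*

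**What the plan says.** The primary endpoint is the "time from enrollment in the study to alleviation of all ARVI symptoms, according to the patient's diary". Footnote 1 (primary endpoint) and footnote 2 (time to normalization of temperature) both require a temperature of 37.5°C or less "for 24 hours (without subsequent increase within the observation period". Footnote 1 adds that any remaining symptoms must total no more than 3 points.

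The Observation period section fixes the length of that period: "In total, the patient is observed up for 14 days".

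Under Study design, parents complete the diary twice a day ("daily in the morning and at night they record oral temperature"), and it is the diary "which parents/adoptive parents return back at Visit 3 or 4". The second of those visits is conditional: "If patients still have any symptoms of ARVI/complications of ARVI, then an additional (unscheduled) Visit 4 is held on Day 10 of the observation". The footnote to the Schedule of study procedures repeats the condition: "provided if the patient still experiences the ARVI symptoms/ complications". The Day 14 telephone visit asks about the child's condition, complications and antibiotics. It does not mention temperature readings or symptom scores.

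**The concern.** The endpoint rule refers to 14 days, but no child has diary readings for 14 days, and the number of diary days depends on how the child is doing on Day 6. A temperature rise on Days 7 to 10 can cancel or postpone the event in a child who still had a symptom at Visit 3. The same rise in a child who was symptom-free at Visit 3 leaves no diary trace. The plan gives no common end to the check and no rule for a child with less than 24 hours of normal readings when the diary is returned. The only missing-data rule, last observation carried forward, could treat the unrecorded days as free of rebound.

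At stake are the primary endpoint and the first secondary endpoint. If one arm recovers faster, more of its children leave diary observation early, and its rebounds are less often counted against it.

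**Working it through.** **Windows, from the plan's own days.**

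| Status at Visit 3 (Day 6) | Diary returned | Days of the 14 without diary readings |
|---|---|---|
| No symptom or complication | Day 6 | 14 − 6 = 8 |
| Any symptom or complication | Day 10 | 14 − 10 = 4 |

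Among children who return the diary on Day 6, one who normalises on Day 3 has about 3 days of later readings and one who normalises on Day 5 has about 1 day. One who normalises on the evening of Day 5 or on Day 6 has less than the required 24 hours. Day 6 return for symptom-free children is inferred from the either-or return wording and the conditional Visit 4. No other reading fits the schedule.

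**The plan's figures, used here only for scale.** A two-sided 5% test with 80% power, difference 0.5 day and SD 1.3 days needs 2 × (1.960 + 0.842)² × 1.3² / 0.5² = 106.1 per group by the normal formula. The exact t calculation gives 108 (power 0.803), as stated. With 25% exclusion, 216 / 0.75 = 288. This point leaves those figures unchanged. The standard error of the difference is 1.3 × √(2/108) = 0.18 day.

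**Size of the bias, simple form.** Bias = (difference between arms in the share returning the diary on Day 6) × (late-rebound rate) × (delay if the rebound were seen). All three inputs are assumed, because the documents give none of them.

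- Low: 0.10 × 0.05 × 4 days = 0.02 day.
- High: 0.20 × 0.10 × 4 days = 0.08 day.

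**Size of the bias, by simulation.** Assumed: normal recovery times with SD 1.3 days, a true shift of 0.5 day, and a rebound that adds 3 days and places recovery no earlier than 6.5 days after enrolment. Times are capped at 10 days. A rebound is missed if the child had recovered within 5 days of enrolment (Visit 3). There were 400,000 children per arm. The last three columns give the observed difference minus the full-window difference, in days.

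| Placebo mean | Diary closed at Day 6, Ergoferon / placebo | 2% rebound | 5% rebound | 10% rebound |
|---|---|---|---|---|
| 4 d | 88% / 78% | 0.010 | 0.026 | 0.049 |
| 5 d | 65% / 50% | 0.011 | 0.029 | 0.056 |
| 6 d | 35% / 22% | 0.008 | 0.020 | 0.043 |

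With equal means of 5 days and 10% rebound, the observed difference is −0.004 day, which is zero within simulation error.

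The two calculations together span about 0.01 to 0.08 day. That is 0.01/0.5 = 2% to 0.08/0.5 = 16% of the target effect, and about 0.06 to 0.45 of the standard error. The upper end is generous: it assumes a 20-point gap in Day 6 returns, whereas the simulated gaps are 10 to 15 points.

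**The case against.** The strongest reply is that both blinded arms follow the same rule, so with no drug effect it favours neither. That stands. A reader might infer that the design inflates the type I error; the documents do not support this.

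Four other stronger readings also fail.

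- *Recovered children stop the diary and unrecovered children continue.* Recovery allows a total score of up to 3, while Visit 4 is triggered by any symptom. Some children who meet the recovery definition therefore keep the diary to Day 10. The split is symptom-free versus not, which still depends on outcome. The simulation ignores this and so overstates early returns in both arms.
- *A large share of events lack 24-hour confirmation.* With SD 1.3 days and an assumed mean of 3 to 5.5 days, 16% to 30% of events fall between 4 and 5 days after enrolment. That is a ceiling. The 24-hour requirement applies to temperature only, so the gap affects only children whose temperature settled last and who are symptom-free at Visit 3.
- *Late rebounds are wholly invisible.* The Day 14 call covers condition, complications and antibiotics, concomitant therapy is recorded at Visit 5, and worsening over 14 days is a separate endpoint. These might reveal a recurrence, but they cannot supply the readings that the primary endpoint needs.
- *The Days 2–6 symptom score and its area under the curve fail for want of a Day 6 evening entry.* Nothing requires both entries on Day 6. The children concerned are symptom-free, so a carried-forward score would most likely be zero.

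The document is a protocol summary, and fuller diary instructions may exist elsewhere. If they set a common end date, the summary should state it.

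**Conclusion.** The point holds in limited form. As written, the rule cannot be applied over the stated 14 days, its effective window depends on the child's state at Visit 3, and the 24-hour requirement cannot be confirmed for symptom-free children who normalise within 24 hours of that visit. This rests on the text alone.

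The effect on the estimate is conditional and small: nil without a drug effect, and about 0.01 to 0.08 day in favour of the faster arm if recovery times differ. That range rests on assumed rebound rates, delays, mean recovery times and Day 6 return shares. It is not evidence that the trial result would be wrong. The case for change is that the primary endpoint should be defined identically for every child and that doing so costs little.

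**What to change.** Have every child keep the twice-daily diary through Day 10 whatever the status at Visit 3, with return by post or photo when there is no Visit 4. In footnotes 1 and 2, replace the reference to the observation period by 'through Day 10' for all children. Align the diary-return wording in Study design and in the schedule.

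The cost is four more diary days for children who would have stopped at Day 6, and some missing late entries. No visit, procedure or sample-size change is needed.

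Ending the check at Visit 3 for everyone and censoring incomplete 24-hour periods would also equalise the window, but it is not advisable. With SD 1.3 days, an assumed mean of 3 to 5.5 days to the start of the 24 hours, and Visit 3 at 5 days, P(T > 4) is 22% to 88%. Up to that share of children would be censored and usable Day 7–10 data lost.
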